Cover Page

Title: Stimulating the Brain to Improve Self-Awareness

NCT Number: NCT03370341

Document Date: 9/19/2017

Objectives

The overall goal is to determine whether we can improve Introspective Accuracy (IA), defined as one's ability to correctly evaluate their own skills and abilities, in individuals with schizophrenia by stimulating the rostrolateral prefrontal cortex via transcranial Direct Current Stimulation (tDCS). Participants will undergo two brain stimulation sessions (one active and one sham) approximately one week apart and, after each session, will complete cognitive and social cognitive assessments along with real-time assessments of their performance (i.e., IA). We hypothesize that individuals will more accurately assess their performance immediately following the active brain stimulation session as compared to immediately following the sham session.

Design

The study will utilize a double-blind, crossover design wherein participants will receive both active and sham stimulation in a counterbalanced order.

Methods and Procedures

This study will involve two sessions, completed approximately one week apart. The sessions will be identical except that the first session will include clinical interviews for the purposes of confirming diagnosis and one session will involve active neurostimulation while the other will involve sham stimulation. We will use a double-blind, cross-over procedure so that across participants the sham session will be equally likely to have occurred first or second and so that both participants and experimenters will be unaware of which session includes the active stimulation.

After providing written informed consent, participants will complete clinical measures to confirm diagnosis and to assess current symptomatology. These include:

1. Mini-International Neuropsychiatric Interview (MINI) (Sheehan et al., 1998). The MINI will be administered by trained study personnel. The MINI was designed to assess Axis I disorders as listed in the DSM-IV-TR. This interview will provide a more nuanced evaluation of the participant's clinical history.
2. Structured Clinical Interview for DSM-IV-TR Axis I Disorders, Research Version, Patient Edition (SCID-I-P) (First, Spitzer, Gibbon, & Williams, 2002). The SCID-I-P will be administered by trained study personnel. The SCID-I-P was designed as a structured interviewing tool to assess Axis I disorders as listed in the DSM-IV-TR. The SCID-I-P is considered to be the gold-standard instrument for DSM-IV diagnosis.
3. Positive and Negative Syndrome Scale (PANSS) (Kay et al., 2009). The PANSS will be administered by study staff, who will be trained to gold standard reliability, to assess the severity of positive and negative symptoms in individuals with schizophrenia. The PANSS has good psychometric properties, which include internal consistency reliabilities of .72 for the Positive Scale, .81 for the Negative scale, and .77 for the General Psychopathology Scale. The PANSS demonstrates good construct validity and criterion-related validity. In a study of 51 patients with chronic schizophrenia, the PANSS Positive scale was significantly correlated

($r=.77$, $p<.001$) to the Scale for Assessing Positive Symptoms (SAPS) and the PANSS negative scale was significantly correlated ($r=.77$, $p<.001$) with the Scale for Assessing Negative Symptoms (SANS) (Kay et al., 2009).

Participants will then begin the neurostimulation portion of the session, which will last for 20 minutes. The participant will be set up with the tDCS material that will start real or sham stimulation, and participants will be informed that they may read or otherwise entertain themselves during this portion of the study. The two electrodes of the tDCS will be placed over the left and right rostrolateral prefrontal cortex. For active stimulation the electrical current will be initially increased in a ramp-like fashion over several seconds (5 seconds) until reaching 1.5mA, and stimulation will be maintained for 20 minutes until it ramps down (5 seconds). For sham stimulation, the electrical current will be increased in a ramp-like fashion over several seconds (5 seconds) until reaching 1.5mA to mimic the sensation present during the first 5 seconds of real stimulation, and then stimulation will be stopped without the participant knowing. The total duration of the sham tDCS will be identical to the active condition in order to appropriately blind the procedure.

Following the neurostimulation portion, the participant will be asked to sit quietly for 30 minutes. After that time has elapsed, the participant will complete the following behavioral measures in a random order:

1. Wisconsin Card Sorting Task (WCST) (Heaton, Chelune, Talley, Kay & Curtiss, 1993). The WCST is a widely used measure of executive function that requires participants to match a presented card to one of four stimulus cards. There are several ways in which the card could be successfully sorted but participants are not informed of the criterion they should use to match the card. Instead, feedback is given after each sort (i.e. correct or incorrect), and participants must use this information to adjust their responses. 10 minutes.
2. Emotion Recognition 40, Degraded Stimuli (ER-40D; Kohler, Turner, Bilker, Brinsinger, Siegel, Kaneshiro, Gur, 2003). The ER-40 is a standardized, computer administered measure of facial affect recognition ability. It includes 40 color photographs of faces expressing 4 basic emotions (i.e. happiness, sadness, anger or fear) and neutral expressions. Participants view one face at a time and are asked to choose the correct emotion for each face. For this version, facial stimuli are digitally blurred in order to make the expressions more difficult to identify. 3 minutes
3. MATRICS Consensus Cognitive Battery - Brief (MCCB-B; Nuechterlein et al., 2008). Trained study staff will administer the MCCB-B to all participants to obtain an estimate of level of cognitive functioning. The MCCB is considered the gold standard cognitive assessment in schizophrenia research and assesses the following domains: Speed of processing, working memory, and verbal learning. 15 minutes.
4. Emotion Recognition Signal Detection Task (ER-SDT; Tsoi et al., 2008). The ER-SDT is a task of emotion recognition that utilizes a signal detection framework. Participants will view 5 different series, or blocks, of 60 emotional faces. For each block, a target emotion (i.e. happy, sad, anger, fear or neutral) will be identified, and participants will be asked to view each face and determine if that face is or is not displaying the target emotion. Following each decision, participants will rate their confidence in the accuracy of that decision on a 4-point scale from "probably wrong" to "probably right." 20 minutes

IA procedure: For all behavioral tasks, participants will self-evaluate their performance in order to obtain estimates of IA. For the WCST, ratings of confidence in correctness are performed after each sort in the 64-card WCST. For the ER-40D, ratings will be performed after each of the 40 trials. For our cognitive assessment battery, the MCCB, performance will be rated after each of the 5 tests. As noted, for the ER- SDT task, participants will self-evaluate their correctness after each item.

At the end of the session, we will ask participants to report which session they believed they just received. This will allow us to assess the success of our blinding procedure.

Statistical Analysis Plan

Repeated Measures ANOVAs will be used to compare indices of neurocognitive and social cognitive IA between stimulation conditions.

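### Do the 30-minute rest before any self-rating and the unstated unit of task-order randomisation undermine the active-sham comparison?

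*Combined protocol and SAP*

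**What the plan says.** The Objectives state the hypothesis that participants will "more accurately assess their performance immediately following the active brain stimulation session as compared to immediately following the sham session". In that section the assessments come after each session, so "session" there reads most naturally as the stimulation itself.

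Methods and Procedures gives a 20-minute stimulation portion and adds: "The total duration of the sham tDCS will be identical to the active condition". It continues: "Following the neurostimulation portion, the participant will be asked to sit quietly for 30 minutes". After the rest, "the participant will complete the following behavioral measures in a random order": the Wisconsin Card Sorting Task (WCST, 10 minutes), the degraded emotion recognition task (ER-40D, 3 minutes), the brief MATRICS battery (MCCB-B, 15 minutes) and the emotion recognition signal detection task (ER-SDT, 20 minutes).

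Under IA procedure: "For all behavioral tasks, participants will self-evaluate their performance in order to obtain estimates of IA". The ratings are made within the tasks.

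On the two visits, Methods and Procedures says: "The sessions will be identical except that the first session will include clinical interviews". The same sentence gives active versus sham as the only other difference. Task order is not mentioned.

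The Statistical Analysis Plan is one sentence: "Repeated Measures ANOVAs will be used to compare indices of neurocognitive and social cognitive IA between stimulation conditions". It has no term for task order or time since stimulation.

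**The concern.** Two things look wrong.

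- **Timing.** The hypothesis speaks of the moment right after stimulation, yet no IA rating is planned in the first 30 minutes. A positive or null result reported in the hypothesis's words would describe a time that the trial does not observe.
- **Task order.** The text gives no unit for the random order. It could be drawn once per participant or afresh at each session. If it is redrawn, a participant may do the same task early in one session and late in the other. Should IA change with fatigue or practice, that would add noise to a within-person comparison, and the analysis has no term to absorb it.

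**Working it through.** The documents give no total assessment time, sample size or power figure, so there is no stated figure to reproduce. The inputs are the rest and task durations in Methods and Procedures.

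**1. The window.** Task time is 10 + 3 + 15 + 20 = 48 minutes, so ratings run from minute 30 to minute 30 + 48 = 78 after the stimulation period ends. This assumes no breaks and that the durations include the ratings. If the 64 + 40 + 5 = 109 ratings on the WCST, ER-40D and MCCB-B are extra, at an assumed 1 to 3 seconds each, they add 109 to 327 seconds and the window ends at about 80 to 83 minutes.

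**2. Validity of the contrast.** Let IA at time t after the stimulation period be g(t) under sham and g(t) + τ(t) under active. The rest and the length of the stimulation period are the same in both conditions, so at equal t the difference is τ(t) and g(t) cancels. The trial estimates τ over roughly 30 to 78 minutes. There is only one assessment block per session, so the analyst has no other time point to choose.

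**3. Order redrawn at each session, drift only.** Each other task precedes a given task with probability 1/2, and each pair of others both precede it with probability 1/3. The start-time variance is therefore

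V = Σd²/4 + (1/6)Σdᵢdⱼ, with sums over the other three tasks and each pair counted once.

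For the WCST: V = (9 + 225 + 400)/4 + (45 + 60 + 300)/6 = 158.5 + 67.5 = 226. The between-session difference in start time has variance 2V = 452 and SD 21.3 minutes. Its mean is 0 for every task, because both sessions draw from the same distribution.

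Suppose IA drifts linearly by D over the 48 minutes, with D in SDs of the within-person difference without timing effects. The added share of contrast variance is (D/48)² × 2V. For the WCST at D = 0.5: 0.25/2304 × 452 = 4.9%.

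| Task | Start range (min) | Mean absolute shift (min) | SD of shift (min) | D = 0.25 | D = 0.5 | D = 1.0 |
|---|---|---|---|---|---|---|
| WCST | 30-68 | 16.8 | 21.3 | 1.2% | 4.9% | 19.6% |
| ER-40D | 30-75 | 19.3 | 24.1 | 1.6% | 6.3% | 25.1% |
| MCCB-B | 30-63 | 14.9 | 18.7 | 1.0% | 3.8% | 15.2% |
| ER-SDT | 30-58 | 12.4 | 15.6 | 0.7% | 2.6% | 10.5% |

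The start ranges and mean absolute shifts come from enumerating all 24 orders and all 24 × 24 pairs. A given task starts at the same time in both sessions with probability 1/6.

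**4. Drift and fading together.** Let f be the drift slope in both sessions and a the slope of the stimulation effect, present only in the active session.

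- Order kept: timing adds a²V to the contrast variance.
- Order redrawn: timing adds (a + f)²V + f²V.
- Excess from redrawing: 2f²V + 2afV = 2fV(f + a).

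The table is the case a = 0. For the WCST at D = 0.5, the excess is 4.9% at a = 0, 9.8% at a = f, zero at a = −f and −4.9% at a = −2f. With fading alone (f = 0) the excess is zero. Keeping one order is therefore not always the more precise choice.

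**The case for a change.** The case for a change is that both gaps are real and cheap to close. Reading "session" as the whole visit does not rescue the hypothesis, because the Objectives place the assessments after it. Reading the adverb as meaning the same day is possible, but the text does not say so. The sentence on identical sessions does not name task order, and two visits that each use a fresh random order could also be called identical. Staff could in good faith do either. The remedy would be a wording edit and one stored order per participant.

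The textual points stand: the hypothesis is loosely worded and the unit of randomisation is not given. What does not follow is any harm to the trial. Anyone reading Methods and Procedures sees when IA is measured, and rewording the Objectives would change no estimate. On order, a literal reading of the two-item list of differences already implies that order is kept, in which case the noise from redrawing is zero. The case for requiring a kept order on grounds of precision also fails as a general claim, since the sign of the effect depends on two slopes that the documents do not give.

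**Conclusion.** No change to the plan follows. The timing point is loose wording: ratings fall at about 30 to 78 minutes on nominal durations, both conditions share the delay, and the active-sham contrast is valid for that window. No view is taken here on what the delay should be.

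The task-order point is a missing detail that the description of identical sessions arguably settles. Even if order were redrawn, there would be no bias. With no fading, the variance cost is 0.7 to 6.3% for assumed drifts of 0.25 to 0.5 SD. It reaches 25.1% only for an assumed full-SD drift, and then only for the 3-minute ER-40D. With fading, the cost may be larger, zero or negative. All these percentages need an assumed redraw and an assumed linear drift in the accuracy of self-rating (not merely in task performance), and the documents support neither.

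### Could the WCST confidence ratings be taken after the participant has already been told whether the sort was correct?

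*Combined protocol and SAP*

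**What the plan says.** The document is a combined protocol and SAP. Under Objectives it defines IA as a person's "ability to correctly evaluate their own skills and abilities". The IA procedure gives the source of the measure: "For all behavioral tasks, participants will self-evaluate their performance in order to obtain estimates of IA".

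Two statements bear on the WCST:

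- **The rating (IA procedure):** "For the WCST, ratings of confidence in correctness are performed after each sort in the 64-card WCST".
- **The feedback (Methods and Procedures, WCST item):** "feedback is given after each sort (i.e. correct or incorrect), and participants must use this information to adjust their responses".

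For the other three tasks the document describes ratings but no feedback:

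- **ER-40D:** "For the ER-40D, ratings will be performed after each of the 40 trials".
- **MCCB:** "performance will be rated after each of the 5 tests".
- **ER-SDT:** "Following each decision, participants will rate their confidence in the accuracy of that decision on a 4-point scale".

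The Statistical Analysis Plan consists of one sentence. It compares neurocognitive and social cognitive IA indices between stimulation conditions by repeated measures ANOVA. It does not list the indices, say which task feeds which index, or say how ratings are combined.

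**The concern.** The WCST is the only one of the four tasks described as telling the participant, trial by trial, whether the response was right. The rating and the feedback are both timed to the end of the sort, and no sentence orders them or says that feedback is held back until the rating is recorded.

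The order matters. Someone who has just heard that the sort was wrong, and is then asked how confident they are that it was right, need only report what they were told. The rating would then reflect attention to the feedback, or memory of it. Agreement between rating and outcome would tend to be high in both the active and the sham session, leaving little room for the hypothesised difference. Feedback cannot be dropped to avoid this, because the task depends on it. The WCST also supplies most of the ratings that could be called neurocognitive, so a flaw there would seem to reach a large part of the outcome.

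**Working it through.** The plan gives no figure on this point, so there is none to reproduce. The check is a reading of the text plus a count of ratings.

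**What order does the text allow?**

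| Order | Consistent with the rating sentence? | Consistent with the feedback sentence? | Consistent with the stated purpose of the rating? |
|---|---|---|---|
| Sort, rating, feedback | Yes | Yes | Yes: the participant judges an outcome not yet known |
| Sort, feedback, rating | Yes | Yes | No: the outcome has been disclosed, so little is left to judge |

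Both orders satisfy the two timing statements. Only the first satisfies the purpose given in the IA procedure and the definition under Objectives. Two further features point the same way:

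- The WCST item under Methods and Procedures describes how the instrument works in general. The rating is an addition made by this study, described in the IA procedure. Use of the same time point in both places does not show that the rating comes second.
- For the ER-SDT, the closest parallel, the rating is tied directly to the decision.

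**How many ratings would be at issue under the second order?** Counts per session, from the IA procedure and the task descriptions:

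- WCST: 64
- MCCB: 5
- ER-40D: 40
- ER-SDT: 5 blocks × 60 faces = 300

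If the WCST and MCCB are grouped as neurocognitive (an assumption, based on the WCST being described as a measure of executive function):

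64 / (64 + 5) = 64/69 = 0.928, about 93%.

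Across all four tasks:

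64 / (64 + 5 + 40 + 300) = 64/409 = 0.156, about 16%.

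The other 409 − 64 = 345 ratings come from tasks with no described feedback and are unaffected under either order.

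Neither percentage is a share of influence on the result. The SAP compares indices and does not say that ratings are pooled across tasks. Counted by task, the WCST is one of four, or one of two within the assumed neurocognitive group.

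**Which way would the error go?** The protocol states that the sessions are identical apart from the first-session interviews and the stimulation condition, so any order used in one session would be used in the other. With A and S for the WCST index after active and sham, post-feedback rating would be expected to push both toward the same high value and shrink A − S toward zero. How close to ceiling they would come cannot be derived, because the document gives neither a WCST rating scale nor a definition of the index.

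**The case for a change.** The strongest case for a change is that intent is not procedure. Someone setting up the task from this text could use either order and still comply. The WCST is the task where order matters most, yet nothing is said about it. Ratings taken after feedback could not be repaired later, and one sentence would remove the doubt at almost no cost.

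Part of this stands. The order is not written down, and the validity of the WCST index depends on it. Confirming how the task is run is a reasonable question to put to the study team.

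The rest does not carry the case to a required change. It needs a team that designed the ratings to measure self-evaluation to disclose the answer before asking for the evaluation. Nothing in the document indicates that they did or would. A forecast of near-ceiling accuracy under the procedure as written treats one of two permitted orders, and the less natural one, as if it were prescribed. A remedy based on reordering screens also assumes a computerised WCST; the document describes the ER-40 as computer administered but does not state the WCST format. Excluding sessions rated after feedback presumes that such sessions exist, and losing one of a participant's two sessions would break that person's active–sham comparison on the WCST.

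**Conclusion.** The concern does not call for a change to the plan. The observation is accurate: rating and feedback share a stated time point, and their order is not given. But the plan contains no instruction to rate after feedback, and its own definition and purpose for the ratings favour rating first. What is missing is a detail of task administration that investigators measuring self-evaluation would be expected to supply correctly.

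The conditional stake is limited to 64 ratings per session on one of four tasks: 93% of ratings under an assumed neurocognitive grouping, 16% overall. The likely direction is toward no difference between conditions, not toward a spurious benefit.

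This conclusion rests on two assumptions: that the team follows the natural order, and that the order is the same in both sessions. The second is supported by the protocol's statement on identical sessions. The first is an inference from wording and purpose. Evidence that ratings were in fact taken after feedback would change the assessment of the WCST index, but the document offers none.

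### Should participants also guess their stimulation condition before the tasks, because the only planned blinding check comes after them?

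*Combined protocol and SAP*

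**What the plan says.** All references are to the combined protocol and SAP. In Methods and Procedures, each session has 20 minutes of active or sham stimulation, 30 minutes of quiet rest, and then four tasks in random order. Sham is a 5-second ramp to 1.5 mA, intended "to mimic the sensation present during the first 5 seconds of real stimulation, and then stimulation will be stopped without the participant knowing". Under the IA procedure, participants rate their own performance in all four tasks, and the Wisconsin Card Sorting Task (WCST) also gives feedback after each sort.

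The blinding question closes that section: "At the end of the session, we will ask participants to report which session they believed they just received". Its purpose is given as follows: "This will allow us to assess the success of our blinding procedure". The protocol also states: "The sessions will be identical except that the first session will include clinical interviews" (the other stated difference being active versus sham stimulation). The question is therefore asked in both sessions, and each participant gives two guesses.

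No guess is scheduled between stimulation and the tasks. The Statistical Analysis Plan is one sentence on comparing IA between conditions and does not mention the guesses.

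**The concern.** The sham has to hide a difference in sensation: a few seconds of current against 20 minutes. A guess taken after the whole task battery mixes memory of that sensation with the participant's impression of how the tasks went. If guesses exceed chance, the reader cannot tell a failed sham from inference based on performance. If task impressions point the wrong way, they could hide real recognition.

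This seems to matter more here than in a trial with an externally measured outcome. IA is built from participants' own ratings, so a belief about allocation could move the outcome directly. If IA improved and guesses were above chance, an expectancy explanation would be hard to exclude, and a pre-task guess cannot be collected afterwards. The 30-minute rest looks like a free place to ask.

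**Working it through.** **Inputs from the documents.** Task times are 10 (WCST), 3 (ER-40D), 15 (MCCB-B) and 20 (ER-SDT) minutes. Self-ratings number 64, 40, 5 and 5 × 60 = 300 respectively.

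- Task time: 10 + 3 + 15 + 20 = 48 minutes.
- Self-ratings before the guess: 64 + 40 + 5 + 300 = 409.
- Nominal gap from end of stimulation to the guess: at least 30 + 48 = 78 minutes.

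The plan has no figure of its own to reproduce: it gives no sample size, effect size or test of the guesses.

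**Assumed for illustration.** N = 20, 30 or 40, with an exact two-sided 5% binomial test against 50%. The upper tail rejects at 15/20, 21/30 and 27/40 or more, with probability 2.1%, 2.1% and 1.9% under pure chance. All rates below are upper-tail rejections, in that order of N.

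**1. False alarms with a perfect sham.** Suppose every participant guesses at the end of session 2 from which session felt better, with standardised paired difference dz. Then P(correct) = Φ(dz). A practice gain of m SD between sessions gives P = Φ(m + dz) in one order and 1 − Φ(m − dz) in the other, with N/2 participants per order.

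| dz | m = 0 | m = 0.5 | m = 1.0 |
|---|---|---|---|
| 0.25 | 12.3 / 17.3 / 20.6% | 8.6 / 12.3 / 14.8% | 2.3 / 3.3 / 4.0% |
| 0.50 | 38.4 / 54.8 / 66.1% | 29.4 / 44.3 / 55.3% | 10.4 / 17.6 / 23.7% |

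For the session-1 guess, P(correct) = Φ(d/2). At d = 0.25 this is 0.550, with false alarms of 5.5 / 6.9 / 7.5%. At d = 0.5 it is 0.599, with 12.3 / 17.3 / 20.6%.

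**2. Masking.** Let a share u truly recognise the condition. If the rest guess at random, P = u + (1 − u)/2. If the rest are misled by the tasks at dz = −0.25, P = u + (1 − u)Φ(−0.25), where Φ(−0.25) = 0.401.

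| u | P, rest random | Detection | P, rest misled | Detection |
|---|---|---|---|---|
| 0.20 | 0.600 | 12.6 / 17.6 / 21.1% | 0.521 | 3.2 / 3.6 / 3.6% |
| 0.38 | 0.690 | 37.9 / 54.1 / 65.3% | 0.629 | 18.8 / 27.2 / 33.4% |

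The first detection column is also the performance of a pre-task guess with no task influence at all.

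**3. What a chance result excludes.** If exactly half are correct, the exact 95% intervals are 27.2–72.8%, 31.3–68.7% and 33.8–66.2%. With non-recognisers guessing at random, the largest compatible recognising share is 2 × upper limit − 1 = 46%, 37% and 32%. These depend only on N, so they hold equally for a guess at any time.

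**4. Would a pre-task guess in session 2 be clean?** Suppose participants give the opposite of a session-1 belief formed from its tasks at d = 0.5. If all do so, 59.9% are correct under perfect blinding, with false alarms of 12.3 / 17.3 / 20.6%. If half do so, 54.9% are correct, with 5.5 / 6.8 / 7.4%. Only the session-1 pre-task guess is fully free of task experience.

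**The case for a change.** The strongest case for a change is that the extra item is cheap, fits into time already scheduled, leaves stimulation and tasks untouched, and supplies information that is lost for good if not collected. The end-of-session question already raises allocation before session 2, so any added priming falls mainly in session 1. On the arithmetic, a moderate felt difference (dz = 0.5, no practice effect) would wrongly signal unblinding in 38% to 66% of trials.

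Part of this stands. A post-task guess cannot isolate sensory masking, and an above-chance result would be ambiguous. Three things weaken the case for acting on it.

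- The hypothesis in Objectives is that self-assessment becomes more accurate, not that the active session feels better. Neither the size nor the direction of a felt difference has support in the documents, and the false-alarm range of about 2% to 66% shows only what is possible.
- The weakness of a chance result is mainly one of sample size, which the new item would share. A chance result after every cue has been available is itself some evidence that participants were not unblinded by session end.
- The extra item is cleanest in session 1. That is also where its priming cost falls, and where participants have no earlier study session to compare with, so recognition is plausibly hardest.

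**Conclusion.** No change is needed; the timing of the guess is a fair trade-off. Expectancy acting on self-ratings is the feared mechanism, and a pre-task question would invite it by having participants state a belief about allocation shortly before those ratings. Experienced statisticians could reasonably decline to put the main comparison at risk to sharpen an ancillary check. Asking at the end keeps the question away from the outcome in session 1 and still measures belief formed from all cues, which is a legitimate reading of whether blinding succeeded.

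The SAP's silence on the guesses is a gap that analysts can fill sensibly by reporting the proportion correct with exact intervals, by condition and session. An above-chance result should then be read as belief from all cues, not as proof that the sham failed. A chance result should be read as modest reassurance: at the assumed sizes of 20, 30 and 40 it would leave up to 46%, 37% and 32% recognition unexcluded, wherever the question is placed.

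All rates rest on assumed sample sizes and assumed felt differences. The IA estimate itself is unaffected by when the guess is analysed or how it is read.

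### The SAP names no session or order term for a two-session crossover whose sessions differ: if IA shifts between sessions, a condition-only ANOVA loses power when orders balance and is biased when they do not

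*Combined protocol and SAP*

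**What the plan says.** The whole analysis plan, under Statistical Analysis Plan, reads: "Repeated Measures ANOVAs will be used to compare indices of neurocognitive and social cognitive IA between stimulation conditions". Stimulation condition is the only model term named.

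The Design section sets up a crossover in which "participants will receive both active and sham stimulation in a counterbalanced order". Methods and Procedures adds that "across participants the sham session will be equally likely to have occurred first or second", but describes no method for securing equal numbers in the two orders among those who complete both sessions.

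On timing and content, Methods and Procedures says: "This study will involve two sessions, completed approximately one week apart". It also says: "The sessions will be identical except that the first session will include clinical interviews for the purposes of confirming diagnosis", the other stated difference being whether stimulation is active or sham. The same behavioural tasks and self-ratings follow stimulation in both sessions.

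For the Wisconsin Card Sorting Task (WCST), "feedback is given after each sort (i.e. correct or incorrect), and participants must use this information to adjust their responses". Under the IA procedure, "ratings of confidence in correctness are performed after each sort in the 64-card WCST".

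**The concern.** In a two-period crossover, each participant's active-minus-sham difference contains any shift between session 1 and session 2, with a sign that depends on the order received. Counterbalancing cancels that shift from the average only if the two orders are equally filled. Even then, the shift adds to the spread of the differences unless the model removes it.

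A shift is plausible here, and it could reach IA itself and not only task performance. By session 2 a participant has already made 64 WCST sorts, each with a confidence rating and right/wrong feedback, which is practice at judging one's own correctness. No such feedback is described for the other tasks, so the shift may differ between indices. Session 1 also carries the interviews. None of this establishes a session effect, and the documents do not give its size.

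At stake are power in a study whose single hypothesis is an active-versus-sham difference in IA and, if completed orders are unequal, the correctness of the estimate. An unstated model also leaves the choice of adding or dropping session until after the data are seen.

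**Working it through.** **Inputs.** From the documents: two conditions, two sessions, intended 1:1 order, repeated measures ANOVA between conditions. Not given: sample size, alpha, variance, effect size, dropout and session shift, so the plan has no figure to reproduce. Assumed: two-sided alpha 5%; N = 30 (also 20, 40, 60); SD 1 for the within-person difference with the session shift removed; session shift π from 0.1 to 1.0 of that SD; stimulation effect τ = 0.53 SD at N = 30, which gives 80% power when π = 0.

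**Model.** For each participant, d = active − sham = τ + πs + e, with s = +1 if active came second and −1 if first, and SD(e) = 1. Let n₁ have active second and n₂ active first, with N = n₁ + n₂.

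**Condition-only ANOVA.** With two levels this is the paired t test on N − 1 df.

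- Bias = π(n₁ − n₂)/N, which is zero when orders balance.
- With balance, the expected variance of d is 1 + π²N/(N − 1). At N = 30 and π = 0.5 it is 1 + 0.25 × 30/29 = 1.259, and √1.259 = 1.12, so the standard error is 12% too large. At π = 0.25 it is 3% too large, and at π = 1.0 it is 43%.
- Rejection rates are exact: the mean of d is normal and independent of the sum of squares, which is noncentral chi-square on N − 1 df with noncentrality 4π²n₁n₂/N.

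**Session-adjusted analysis.** The estimate is the simple average of the two order-group means of d. Its standard error is ½√[s²(1/n₁ + 1/n₂)], with s² pooled within orders on N − 2 df. The shift cancels from the estimate and from s².

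**Results, N = 30**

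| | π = 0.1 | π = 0.25 | π = 0.5 | π = 1.0 |
|---|---|---|---|---|
| 15:15, condition only, power | 80% | 78% | 73% | 50% |
| 15:15, condition only, type I error | 4.9% | 4.4% | 2.9% | 0.6% |
| 15:15, session adjusted, power | 80% | 80% | 80% | 80% |
| 18:12, condition only, bias (SD) | 0.02 | 0.05 | 0.10 | 0.20 |
| 18:12, condition only, type I error | 5.0% | 5.1% | 5.3% | 4.6% |
| 20:10, condition only, bias (SD) | 0.03 | 0.08 | 0.17 | 0.33 |
| 20:10, condition only, type I error | 5.3% | 6.5% | 10.1% | 17.4% |

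The session-adjusted test has 5% type I error and no bias in every column. Simulations of the same model agree within simulation error.

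**Other sample sizes.** Balanced power is within 1 point of the N = 30 figures for N = 20 to 60. The unequal-order results depend on N. For π = 0.25, 0.5 and 1.0, condition-only type I error is:

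- about 5.5%, 6.6% and 7.5% at 13:7 (N = 20);
- about 7.6%, 14% and 29% at 27:13 (N = 40);
- about 6%, 8% and 11% at 36:24 (N = 60), the same 60:40 ratio that is near nominal at N = 30.

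**Weighting.** If order enters the ANOVA but condition is tested with Type II weights, the estimate is still the raw mean of d, so the bias stays while the error term shrinks. At 18:12, type I error is then 5.8%, 8.3% and 18.5% for π = 0.25, 0.5 and 1.0.

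**Cost of adjusting when π = 0.** At 18:12 the adjusted standard error is ½√(1/18 + 1/12) = 0.186 against 1/√30 = 0.183, and power is 78%. At 20:10 it is ½√(1/20 + 1/10) = 0.194, and power is 75%.

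**The case against.** The SAP is silent; it does not specify the wrong model. A repeated measures ANOVA with order as a between-subject factor fits its sentence, so harm requires the analyst to choose the weaker reading. That is correct, and the defect is one of specification.

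Counterbalancing already protects against the serious consequence. At balance the condition-only contrast is unbiased and the test conservative, so no excess of false positives arises. Splits as uneven as 20:10 are unlikely: even simple 50:50 allocation gives that or worse only about 10% of the time at N = 30, and 27:13 or worse about 4% of the time at N = 40. Averaged over simple 50:50 allocation, type I error is 5%. This also stands. The bias concerns the split actually achieved, and marked imbalance would need dropout, exclusions or loose allocation. The lost power does not depend on imbalance: under simple 50:50 allocation at N = 30 it is 78%, 71% and 51% at π = 0.25, 0.5 and 1.0, against about 79% adjusted.

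The evidence for a session effect is limited. Twenty minutes of stimulation and 30 minutes of quiet sitting separate the interviews from the tasks, and the feedback route applies to one task of four. The 50% power figure needs a shift of a full SD, which nothing in the documents supports. These points limit the likely size, but the model can allow for a shift at little cost.

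**Conclusion.** The point holds and should be fixed. No session or order term is named anywhere in the documents, and the design gives reason to expect that the sessions may differ.

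The main consequence under the planned balance is lost power: at most 2 points for shifts up to 0.25 SD, about 7 points at 0.5 SD and 30 points at 1.0 SD. Bias of π(n₁ − n₂)/N arises only if completed orders are unequal. Type I error is near nominal at 18:12 with N = 30 and rises at stronger imbalance, or at the same ratio with larger N.

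That the term is missing is certain. The sizes are conditional: they rest on an assumed N, a range of assumed session shifts and normal errors with equal variance in both orders. Confidence in the practical impact is therefore medium.

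**What to change.** State in the SAP that each IA index is analysed with condition (active, sham), session (1, 2) and order (active first, sham first), and that the session-adjusted active-minus-sham contrast is the result reported. Either of two models will do:

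- a linear mixed model with a random participant intercept; or
- for complete pairs, the repeated measures ANOVA with order as a between-subject factor, where the condition-by-order interaction carries the session effect. Specify equal weighting of the two orders (Type III, effect-coded).

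On simulated complete pairs at 15:15, 18:12 and 20:10 (one data set each), the two gave the same estimate and standard error to four decimals. They differ for participants with only one session, so the SAP should name which is used. Report the achieved order split.

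The change is short and needs only the record of which session was active, which the condition comparison requires anyway. It costs one error degree of freedom and, if there is no session shift, about 2 points of power at 18:12 and 5 at 20:10 (N = 30). The added terms do not remove carryover from one session to the next.
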